7. TABLE OF EVENTS

[figure not shown]
Table 3: Table of Events

Event	Screen	Treatment Period						Follow-up period ^w			
	Baseline ^a	Day 1 ^k	Day 4 (+ 2 days) ^k	Day 7 (+ 2 days) ^k	Day 15 (± 2 days)	Day 21 (± 2 days)	Day 28 (± 2 days)	Day 90 (±14 days)	Day 180 (±14 days)	Hospital Discharge ^v (if applicable)	Early Termination ^b
Study Entry and General Assessments											
Study Informed Consent	X	-	-	-	-	-	-	-	-	-	-
Inclusion/Exclusion Assessment	X	-	-	-	-	-	-	-	-	-	-
Pre-ICF rRT-PCR (or other approved test per institutional practice) results confirming SARS-CoV-2	X	-	-	-	-	-	-	-	-	-	-
Demographics/Medical history	X	-	-	-	-	-	-	-	-	-	-
Treatment and Study Required concomitant medications											
Phase II only: Randomization to CYNK-001 or Best Supportive Care (1:1 ratio) after treatment eligibility is confirmed	X	-	-	-	-	-	-	-	-	-	-
CYNK-001 IV infusion ^{c,d}	-	X	X	X ^e	-	-	-	-	-	-	-
Best supportive care - Control group (Phase II only)	-	Control group to receive Best Supportive Care only						-	-	-	-
Acetaminophen 650mg PO pre- and post-medication ^d	-	X ^{f,k}	X ^{f,k}	X ^{f,k}	-	-	-	-	-	-	-

CYNK-001
Celularity Inc

[figure not shown]
CYNK-001-COVID-19

[figure not shown]

[figure not shown]

[figure not shown]
CYNK-001
Celularity Inc

CYNK-001-COVID-19

8. SELECTION AND WITHDRAWAL OF SUBJECTS

8.1. Subject Inclusion Criteria

1. Subject has confirmed positivity for SARS-CoV-2 as measured by rRT-PCR or other approved test to detect SARS-CoV-2 per institutional practice.
2. Subject is experiencing any symptom/clinical sign of COVID-19 illness or has a positive disease-related chest x-ray/CT scan at screening.
3. Subject is ≥ 18 years of age at the time of signing the Study informed consent form (ICF).
4. Subject understands and voluntarily signs the Study ICF prior to any study-related assessments/procedures are conducted.
5. Subject is willing and able to adhere to the study schedule and other protocol requirements.
6. $\text{SpO}_2 \geq 88\%$ on room air; oxygen is permitted as delivered by nasal cannula and/or face mask at any flow rate to achieve this SpO_2 . Subjects must have an $\text{SpO}_2 \geq 92\%$ if on supplementary oxygen.
 - *(Note: Once eligibility is confirmed, to initiate CYNK-001 treatment, an increase of supplemental oxygen of greater than or equal to 50% from baseline/screening resulting in oxygen use of greater than 8L -or- a change in mode of supplemental oxygen delivery with the intention to deliver oxygen more frequently requires consultation with the medical monitor)*
7. Ability to be off immunosuppressive drugs for 3 days prior to infusion, unless clinically indicated. Steroids are permitted if clinically indicated and at the discretion of the treating physician. If clinically indicated, careful consideration should be taken regarding the timing and tapering of high-dose steroids.
8. Female of childbearing potential (FCBP)* must not be pregnant and agree to not becoming pregnant for at least 28 days following the last infusion of CYNK-001. FCBP must agree to use an adequate method of contraception during the treatment period.
 - a. *FCBP is a female who: 1) has achieved menarche at some point, 2) has not undergone a hysterectomy or bilateral oophorectomy or 3) has not been naturally postmenopausal (amenorrhea following cancer therapy does not rule out childbearing potential) for at least 24 consecutive months (i.e., has had menses at any time in the preceding 24 consecutive months).
9. Male subjects must agree to use a condom during sexual contact for at least 28 days following the last infusion of CYNK-001, even if he has undergone a successful vasectomy.

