6.1.2. Treatment Period (Day 1 to Day 28)

The treatment period begins with the administration of study drug on Study Day 1. For those subjects who are allocated treatment to CYNK-001, the initial dose will consist of 150×10^6 cells followed by the second and third doses each of 600×10^6 cells administered intravenously (IV). Subjects will receive a minimum of two and up to three CYNK-001 infusions. CYNK-001 infusions will occur on Study Days 1, 4, and 7. After the first dose, subsequent infusions on Days 4 and 7 will be provided only if no toxicity of Grade 3 and above (either related or unrelated to CYNK-001) is observed for each subject. If any such \geq Grade 3 toxicity is observed, the second and third doses will be delayed up to 48 hours until the noted event is resolved or reduced to Grade 1 toxicity level.

Subjects treated in Phase I will receive all planned CYNK-001 infusions in the inpatient setting and may be discharged one day following the final planned CYNK-001 infusion (i.e., discharged on Study Day 8, where infusions occur on Days 1, 4, and 7). If any dose is delayed, subjects will remain inpatient until one day following the final CYNK-001 infusion.

As part of discharge criteria, the study team should assess for further monitoring of subjects who may be experiencing toxicity of Grade 3 and above (either related or unrelated to CYNK-001) at the time of discharge and consult with the treating physician. The decision to discharge a subject should be in consultation with the treating physician. Physicians should follow best clinical practice to determine appropriate timing of hospital discharge.

Upon discharge, plans should be made for appropriately delegated staff to have telephone contact with subjects every day between hospital discharge through at least Day 15 visit for safety/AE monitoring.

Subjects will be provided with a thermometer, pulse oximeter, and blood pressure monitor for at home collection of temperature, oxygen saturation, and blood pressure with written instructions on their use as well as expectations for self-monitoring. These daily measurements will be reported via telephone to the clinical staff during each daily telehealth visit. During these daily telehealth visits, subjects are to report any new symptoms or worsening of symptoms associated with previously identified adverse events.

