6.1.3. Follow Up Period

The follow-up period is defined from Day 29 to Month 6. Subjects will be followed at 3 months, and 6 months, or until loss to follow-up, death, or withdrawal from study, whichever occurs first.

The study will be conducted in compliance with ICH Good Clinical Practices (GCPs) and in concordance with local Health Authority regulations.

The End of Trial is defined as either the date of the last visit of the last subject to complete the post treatment follow-up, or the date of receipt of the last data point from the last subject that is required for primary, secondary and/or exploratory analysis, as specified in the protocol, whichever is the later date.

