6.3. Dose Limiting Toxicity (DLT) Definition

Known pathologies associated with COVID-19 will be carefully considered and differentiated from potential CYNK-001-related effects in order to identify CYNK-001 related toxicities. Adverse events occurring up to Day 28 from the first dose of the CYNK-001 infusion will be included in the dose-limiting toxicity (DLT) determination.

A DLT is defined as the development of any new (not pre-existing) events:

- Grade 4 or 5 event in any organ system
- Grade 4 > 24 hour (Due to known organ damage associated with the COVID-19) in the following organ systems:
 - Cardiac
 - Pulmonary
 - Hepatic
 - Renal
 - Central Nervous System (CNS)
- Grade 3 or above allergic reaction that is suspected to be related to CYNK-001.
- Grade 3 or above GvHD event occurring within the first 28 days following CYNK-001 infusion (to Study Day 28).
- Grade 3 or above CRS event occurring within the first 28 days following the first CYNK-001 infusion (to Study Day 28).

All above events to be identified in discussion with the clinical study Medical Monitor and reportable to Drug Safety.

The events will be assessed for the first 3 subjects in Phase I and per the study stopping rules for the remaining subjects. Any such findings will be forwarded to the DMC for recommendation, review and confirmation as to whether or not the maximal tolerated dose (MTD) has been exceeded. If the MTD is confirmed by the DMC, no further CYNK-001 administration will occur within that dose level or at any higher dose level. For the remaining 11 subjects, DMC will be convened if the safety stopping rule is met. Overall, in case of 2 out of the 6 subjects had

experienced DLTs in the Phase I portion of this study, the DMC will be convened for safety evaluation.

During Phase II portion of the study, DMC will be convened at midpoint (after 18 subjects have received treatment) to evaluate safety for adverse event of interest such as shock, ARDS, and death in the treatment group versus the control group.

MTD is defined as the highest CYNK-001 dose level wherein it was deemed safe per the defined stopping rules or if the DMC recommends stopping the study due to DLTs suspected to be related to CYNK-001.

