All subjects will be monitored for AEs during the study. **Infusion related reactions (IRRs) will be documented for the first 72 hours of CYNK-001 infusion at every dose.** Assessments may include monitoring of any or all of the following parameters: the subject's clinical symptoms, laboratory, pathological, radiological or surgical findings, physical examination findings, or findings from other tests and/or procedures.

All AEs that occur after any subject has been enrolled, before treatment, during treatment, or within 28 days following the first CYNK-001 infusion (to Study Day 28), whether or not they are related to the study, must be recorded on forms provided by Celularity.

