The Phase II portion of the study is a randomized, open-label, multi-site study. 72 Subjects will be randomized to either CYNK-001 (n=36) or Control group (n=36) with best supportive care alone as defined by the hospital by 1:1 ratio, stratified by age (<45 vs. ≥45 years old).

DMC will be convened at midpoint of Phase II (after 18 subjects have received treatment) to evaluate safety and adverse events of interest such as shock, ARDS, and death in the treatment group versus control group. Adverse events of special interest (AESI) will be identified in collaboration with the sponsor and medical monitor.

Each subject is expected to remain in the study for both, treatment period (Day 1 after first infusion to Day 28) and follow-up period (Day 29 to Month 6) with assessment at 3-month and 6-month after infusion.

The study is divided into 3 study periods: Screening Period, Treatment Period, and Follow-up Period, each with associated evaluations and procedures that must be performed at specific timepoints.

4. General Analytic Considerations

Analysis for Phase I and Phase II will be performed separately.

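### Inclusion 8 requires contraception only to Day 28, 6 to 7 days short of its own no-pregnancy window of 28 days after the last infusion

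*Protocol*

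**What the plan says.** Inclusion 8 in Protocol 8.1 makes two demands of women of childbearing potential. The first is that they "must not be pregnant and agree to not becoming pregnant for at least 28 days following the last infusion of CYNK-001". The second, which follows directly, concerns the method and ties contraception to the treatment period: "at least 28 days following the last infusion of CYNK-001. FCBP must agree to use an adequate method of contraception during the treatment period".

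The treatment period is a defined term. The Section 6.1.2 heading and the synopsis both give it as Day 1 to Day 28. Section 6.1.3 confirms the boundary: "The follow-up period is defined from Day 29 to Month 6". SAP Section 3 uses the same split.

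Inclusion 9, the next criterion, sets the rule for men and runs it from the last dose: "Male subjects must agree to use a condom during sexual contact for at least 28 days following the last infusion of CYNK-001".

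Infusions are planned on Days 1, 4 and 7 (Protocol 6.1.2).

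**The concern.** Inclusion 8 protects a period counted from the last infusion but prescribes the means of protection for a period counted from the first. Because the last infusion normally falls about a week after the first, the second period ends before the first does.

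In the days between, a treated woman has undertaken not to become pregnant, but the protocol no longer requires her to use contraception. A site or consent form that repeated only the second sentence would tell her that the requirement ends at Day 28. The consent pages are not in the public copy, so whether that happened cannot be checked.

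What is at stake is participant protection and the consistency of an eligibility criterion. Nothing in the endpoints, sample size or analysis depends on it.

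**Working it through.** The plan states no figure for this gap, so there is none to reproduce. The check is study-day arithmetic.

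**Inputs**

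- End of required contraception: Day 28 (Protocol 8.1, read with 6.1.2 and 6.1.3).
- Last infusion, planned course: Day 7 (6.1.2). Dose Level -1, given on Days 1 and 7, also ends on Day 7 (6.4).
- Latest third dose: Day 9. Section 6.5 allows a 48-hour delay and Table 3 shows Day 7 with a window of plus 2 days.
- Earliest end of a two-dose course: Day 4, since the third dose can be omitted (6.5, 6.1.4). With the permitted delay of the second dose, this becomes Day 5 or 6.
- A single dose on Day 1 is not a planned course, because 6.1.2 sets a minimum of two infusions. It can arise through withdrawal (6.6.3) or stopped dosing.

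**Counting convention**

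The documents support two ways of counting 28 days from a dose.

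- The protocol equates 28 days from a Day 1 dose with Study Day 28. Section 12.3.1.1 has "within 28 days following the first CYNK-001 infusion (to Study Day 28" and the dose-limiting toxicity definition in 6.3 does the same. The dosing day counts as day 1.
- Ordinary counting leaves the dosing day out. The SAP Section 12 formula (event date minus Day 1 date, plus 1) agrees: 28 days after a Day 1 dose is 28 + 1 = Day 29.

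**Formulas**, with d the study day of the last dose

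- Protocol counting: window ends on Day d + 27; gap = (d + 27) − 28 = d − 1.
- Ordinary counting: window ends on Day d + 28; gap = (d + 28) − 28 = d.

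**Results**

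| Last dose (d) | How it arises | Window ends | Gap after Day 28 |
|---|---|---|---|
| Day 1 | single dose, not planned | Day 28 to 29 | 0 to 1 day |
| Day 4 | third dose not given | Day 31 to 32 | 3 to 4 days |
| Day 5 | as above, second dose one day late | Day 32 to 33 | 4 to 5 days |
| Day 6 | as above, second dose two days late | Day 33 to 34 | 5 to 6 days |
| Day 7 | as planned, or Dose Level -1 | Day 34 to 35 | 6 to 7 days |
| Day 8 | third dose one day late | Day 35 to 36 | 7 to 8 days |
| Day 9 | latest third dose | Day 36 to 37 | 8 to 9 days |

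Every course of two or more doses leaves a gap.

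**Sensitivity to the meaning of treatment period**

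- If the term meant only the dosing days (Days 1 to 7), the gap on the planned schedule would be 34 − 7 = 27 to 35 − 7 = 28 days. Reading it as Day 1 to Day 28 is therefore the more lenient reading.
- Table 3 gives the Day 28 visit a window of plus or minus 2 days. That is a visit window and does not define the period. Even if the period were stretched to Day 30, the planned schedule would still leave 34 − 30 = 4 to 35 − 30 = 5 days.

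**The case against.** The strongest reply is that protection has no hole. The first sentence of Inclusion 8 already binds a treated woman for the full 28 days after her last dose, and keeping that promise implies some means of doing so. This stands, and it limits the seriousness: the duty not to become pregnant never lapses. It does not reconcile the two sentences. The protocol chose to specify contraception separately and gave it an earlier end.

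A second reply is that control subjects must also meet the criteria (6.1.2) and have no infusion date, so the treatment period is the only anchor that works for them. That is a fair reason to keep the treatment period in the sentence. It is no reason to leave out the longer period for those who are infused.

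A third is that other provisions also stop around Day 28. The last pregnancy test is at Day 28 (12.1.12.6), and pregnancy reporting for female subjects runs while on CYNK-001 or to 28 days from first treatment (12.3.1.13). These rules govern monitoring and reporting; they do not set the period in which pregnancy is to be avoided. Inclusion 8 sets that period, and Inclusion 9 follows it.

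Two limits should be acknowledged. Most rows of Table 3 and all its footnotes are absent from the public copy, so a contraception note there cannot be excluded, although it would not change the wording of the criterion. And nothing in the available text shows that reproductive risk differs between Day 28 and Day 35; the point is that the protocol does not match its own window.

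**Conclusion.** The concern holds. As written, Inclusion 8 ends the contraception requirement 6 to 7 days before the end of its own no-pregnancy window on the planned schedule. The range is 3 to 9 days across the two- and three-dose courses the protocol allows. The result rests on treatment period having its defined meaning of Day 1 to Day 28 and on Day 9 as the latest third dose; the one-day spread within each case is the counting convention alone.

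The practical effect is small. The undertaking not to become pregnant covers the gap, no analysis is touched, and SAP Section 15 reports early closure with seven patients dosed in Phase I. It is nevertheless a clear inconsistency in a participant-protection rule. It should be corrected in the protocol and wherever its wording is reused.

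**What to change.** Extend the second sentence of Inclusion 8 so that it reads, in substance: *women of childbearing potential agree to use adequate contraception throughout the treatment period and, where CYNK-001 is given, until at least 28 days after the last infusion.* Make the same change in the consent form if it repeats the sentence.

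On the planned schedule this moves the end of required contraception from Day 28 to Day 34 or 35, and to Day 36 or 37 if the last dose is on Day 9. The gap becomes zero under either counting. The wording agrees with the first sentence and with Inclusion 9, and it still works for control subjects.

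The cost is one clause, with no extra visit, test or procedure. Re-timing the Day 28 pregnancy test and moving the reporting window in 12.3.1.13 to the last dose would be optional alignment; neither is claimed as an error here.

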8.2. Subject Exclusion Criteria

1. Subject requires supplemental oxygen delivered by mechanical ventilation, either invasive or bilevel positive airway pressure.

[figure not shown]
2. Subject admitted to Intensive Care Unit / Pulmonary Acute Care Unit designated area with severe pulmonary pneumonia, ARDS or Sepsis.
3. Subject is pregnant or breastfeeding.
4. Subject has a history of chronic asthma requiring ongoing medical therapy or other chronic pulmonary disease that, at the discretion of the treating physician, would contraindicate participation in this study.
5. Subject has any other organ dysfunction [Common Terminology Criteria for AEs (CTCAE) Version 5.0 Grade 3] that will interfere with the administration of the therapy according to this protocol.
6. Subject has inadequate organ function as defined below at time of Treatment Eligibility Period:
 - a) Subject has aspartate aminotransferase (AST), alanine aminotransferase (ALT), or alkaline phosphatase $\geq 5 \times$ the upper limit of normal (ULN). (It is anticipated that the infection may impact liver.)
 - b) Estimated glomerular filtration rate (eGFR) < 30 mL/min/1.73 m² as calculated using the Modification of Diet in Renal Disease Study equation (Levey, 2006) or history of an abnormal eGFR < 60 . A decline of > 15 mL/min/1.73 m² below normal in the past year prior to infection. (It is anticipated that the infection may impact renal function.)
 - c) Subject has a bilirubin level > 2 mg/dL (unless subject has known Gilbert's Syndrome).
7. Subject has a known sensitivity or allergy to treatment additives or diluent substances of dimethyl sulfoxide (DMSO), PlasmaLyte A or human serum albumin (HSA). Please refer to investigational brochure (IB).
8. Subject has active autoimmune disease other than controlled connective tissue disorder or those who are not on active therapy.
9. Subject is immunocompromised, has known human immunodeficiency virus (HIV) positivity, or has actively been treated with immunosuppressive products prior to being infected with SARS-CoV-2.
10. Subject has known active malignancy, unless the subject has been free of disease for ≥ 3 years from the date of signing the ICF. Exceptions include the following noninvasive malignancies:
 - a. Basal cell carcinoma of the skin
 - b. Squamous cell carcinoma of the skin
 - c. Carcinoma in situ of the cervix
 - d. Carcinoma in situ of the breast
 - e. Incidental histological finding of prostate cancer (TNM stage of T1a or T1b)

[figure not shown]
11. Detection of other respiratory viruses from mucosal surfaces that, at the investigator's discretion, would interfere with the study treatment plan; detection of another respiratory virus is *not in itself* an exclusion criteria unless the investigator believes it would interfere with administration of CYNK-001.
12. Subjects must not have a history of unconsciousness or hemoptysis within 2 weeks of signing ICF.
13. Subjects must not have end stage liver disease and/or cirrhosis.
14. Subject has any significant medical condition, laboratory abnormality, or psychiatric illness that would prevent the subject from participating in the study.
15. Subject has any condition including the presence of laboratory abnormalities which places the subject at unacceptable risk if he or she were to participate in the study.
16. Subject has any condition that confounds the ability to interpret data from the study.

9. TREATMENT OF SUBJECTS

9.1. Description of Study Drug

For full description of CYNK-001, refer to the Investigator's Brochure (IB).

9.1.2. CYNK-001 Overdose

On a per dose basis, an overdose is defined as the following amount over the protocol-specified dose of CYNK-001 assigned to a given subject, regardless of any associated AEs or sequelae:

CYNK-001: 30% over the assigned protocol-specified dose of 600×10^6 cells.

On a schedule or frequency basis, an overdose is defined as anything more frequent than the protocol required schedule or frequency.

Complete data about drug administration, including any overdose, regardless of whether the overdose was accidental or intentional, should be reported in the eCRF. (Refer to [Section 12.3.1.1](#) for overdose reporting requirements).

